- 3) The outcome of self-paced walking with real-time feedback is NOT equal to self-paced walking with internal focus of attention ( $c < b$ )

Secondary null hypothesis: Means of the outcome "ground reaction force loading rate" are equal across the four conditions a) self-paced walking, b) self-paced walking with internal focus of attention, c) self-paced walking with real-time feedback, and d) condition c speed-matched walking. Predefined contrasts are for this outcome concordant with those of the primary hypothesis.

Secondary alternative hypothesis: Means of the outcome "ground reaction force loading rate" are NOT equal across the four conditions a) self-paced walking, b) self-paced walking with internal focus of attention, c) self-paced walking with real-time feedback, and d) condition c speed-matched walking. Two-sided testing will be applied, as knowledge from existing literature is only moderate. Predefined contrasts are for this outcome concordant with those of the primary hypothesis.

Tertiary null hypothesis:

- 1) The agreement of continuous kinematic and kinetic outcomes of the lower limb (see list of outcome parameters) between decline ramp walking and speed-matched decline treadmill walking is lower than 0.75 (ICC).
- 2) The agreement of continuous kinematic and kinetic outcomes of the lower limb (see list of outcome parameters) between decline ramp walking and self-paced decline treadmill walking is lower than 0.75 (ICC).
- 3) The agreement of continuous kinematic and kinetic outcomes of the lower limb (see list of outcome parameters) between incline ramp walking and speed-matched incline treadmill walking is lower than 0.75 (ICC).
- 4) The agreement of continuous kinematic and kinetic outcomes of the lower limb (see list of outcome parameters) between incline ramp walking and self-paced incline treadmill walking is lower than 0.75 (ICC).

Tertiary alternative hypothesis:

[figure not shown]
- 1) The agreement of continuous kinematic and kinetic outcomes of the lower limb (see list of outcome parameters) between decline ramp walking and speed-matched decline treadmill walking is at least 0.75 (ICC).
- 2) The agreement of continuous kinematic and kinetic outcomes of the lower limb (see list of outcome parameters) between decline ramp walking and self-paced decline treadmill walking is at least 0.75 (ICC).

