**Figure: Flow diagram of the progress through the phases of the trial**

## Sample size estimation and study population

As knowledge and studies concerning the effect of real-time feedback during decline walking is missing, sample size calculation based on proven effects is not applicable. Therefore sample size was arbitrary estimated with 25 based on the number of participants included in topic-specific studies, ranging from 14 to 40. Taking into account a drop out of 20% we will recruit 30 participants.

Those healthy participants will be included, according to the following inclusion criteria: 1) age from 18-35 years, 2) body mass index from 18.5 to 29.99 kg/m^2, 3) no chronological joint diseases and/or OA surgery, and 4) no neuro-motor diseases. Participants will be excluded from the analysis in case of 1) non-physiological and non-symmetrical gait patterns, and 2) severe outliers (more than two standard deviations).

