## Examination Procedures

At first, height will be measured with a stadiometer to the nearest 0.5 cm (SECA 213), and weight with a medical scale (Marsden M-420). Furthermore, joint range of motion and functional hamstring flexibility will be assessed. Thereafter, all participants will be equipped with 43 retroreflective markers on bony landmarks and 16 markers on four rigid clusters on thighs and shanks. Five level walking trials will be captured to evaluate if gait pattern is physiological or not. Participants will have to walk on a five-meter ramp with 10° inclination which is equipped with 24 infrared cameras (Vicon, Oxford, United Kingdom) and two force plates (Kistler, Winterthur, Switzerland). After seven left and seven right foot strikes on

the force plates for up and down walking each, the participants will be guided to the Gait Real-time Analysis Interactive Lab (GRAIL, Motekforce Link, Amsterdam, Netherlands), which is located next door. The GRAIL is a dual-belt treadmill equipped with two force plates, a 180° virtual reality screen and a motion capturing system with ten infrared cameras. After the familiarization phase on the treadmill with an inclination of 10° and with matched speed of incline walking, three times a period of 20 seconds will be recorded within 3 minutes. The investigator will explain the self-paced mode of the treadmill to the participant afterwards. The self-paced mode will adapt the belt speed automatically based on the position of the participant on the treadmill. Following a familiarization phase, data will be recorded as before.

This procedure will be repeated on the treadmill with a declination of 10°. Thereafter, the three following tasks will be performed in the order as specified in the sequence list.

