## Outcome parameters

Height, bodyweight and inter-anterior superior iliac spine distance will be measured at the beginning of all sessions. Furthermore, flexibility of hamstrings and triceps surae will be assessed clinically. The primary outcome of this study is the frontal knee range of motion during the stance phase. Stance phase will be defined between heel-strike and toe-off of the observed leg. A second focus is on the ground reaction force loading ratio. Thirdly, the kinematics for the sagittal, frontal and transversal plane for hip, knee and ankle and the external moments for the sagittal and frontal plane for hip, knee and ankle will be assessed as well as step time, step length, step width, cadence and walking speed (table 1).

Area	Outcome Measure
Kinematic	3 planes of hip angle range of motion (°)
	Minimum sagittal hip angle (°)
	Maximum sagittal hip angle (°)
	3 planes of knee angle range of motion (°)
	Minimum sagittal knee angle (°)
	Maximum sagittal knee angle (°)
	Sagittal ankle angle range of motion(°)
	Minimum sagittal ankle angle(°)
	Maximum sagittal ankle angle(°)
	3 planes of pelvis angle range of motion (°)
	3 planes of trunk angle range of motion (°)
	Minimum sagittal trunk angle (°)
	Minimum sagittal trunk angle (°)
Kinetics	First peak load (N)
	Moment of first peak load (%)
	Average loading rate (N s  )
	Maximum loading rate (N sec  )
	Knee joint forces (N/kg)
	3 planes of minimum of hip external moments (Nm/kg)
	3 planes of maximum of hip external moments (Nm/kg)
	3 planes of minimum of knee external moments (Nm/kg)
	3 planes of maximum of knee external moments (Nm/kg)
	Minimum of sagittal ankle external moment (Nm/kg)
	Maximum of sagittal ankle external moment (Nm/kg)

Area	Outcome Measure
	Frontal knee abduction moment impulse (Nm/kg s)
	Frontal knee adduction moment impulse (Nm/kg s)
Spatio-temporal parameters	Walking velocity (m sec  )
	Cadence (steps min  )
	Step length (m)
	Step width (m)
	Stance phase duration (% gait cycle)
	Swing phase duration (% gait cycle)

**Table 1:** List of tertiary outcome parameters

Kinematic data will be time normalized from heel strike to heel strike, kinetic data from heel strike to toe-off. Individual participant data will be expressed as average per condition. Time normalization, data processing and parameter calculations will be done with self-developed scripts in MATLAB 2018a (The Mathworks, Natick, MA, USA).

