## Statistical analysis

All metric parameters will be analyzed with SPSS 26 (IBM Corporation, Armonk, NY, USA). Data will be tested for normality using the Shapiro-Wilk Test, and graphical inspections of Q-Q-plots. Differences between ramp-walking and matched speed / self-paced walking on the inclined / declined treadmill will be analyzed using paired two-tailed t-test and tested for agreement using ICC [3.1, absolute agreement, single measures] with SEM of the ICC. To evaluate differences between the four conditions (decline walking, internal focus of attention, real-time feedback, and matched speed walking), a one-factorial analysis of variance with repeated measures will be used. Contrasts will be employed to test aforementioned pre-specified hypotheses. In view of the legitimization given with the hypothesis, two-sided testing will be applied. One-dimensional statistical parameter mapping (1dSPM) will be used to examine the steady parameters of the gait analysis. All other statistical tests than those related to the primary and secondary hypotheses are considered exploratory and statistical testing will be limited to tests as pre-specified by the hypotheses. Consequently, Bonferroni-Holm method will be used in terms of correcting for multiple testing. Alpha will be set to 0.05; exact p-values will be reported though.

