## **Limitations and problems anticipated**

The condition speed-matched walking cannot be included into the randomization procedure. Due to the nature of the studied conditions, it will neither be possible to conceal the allocation, nor to blind participants or researchers. Another limitation is that different force plates are used for ramp-walking and treadmill walking, as well as the continuous quality of declined treadmill force plate data cannot be guaranteed. Thereby a small systematic error can maybe affect the kinetic outcome. Findings of this study will apply only to healthy young adults.

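### The 2 SD participant exclusion does not say what is screened, would remove valid participants, and can bias the ICC down or up; no analysis with all participants is planned

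*Combined protocol and SAP*

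**What the plan says.** Under *Sample size estimation and study population*, the protocol states: "Participants will be excluded from the analysis in case of" either an abnormal or asymmetric gait pattern, or "severe outliers (more than two standard deviations". This is its only statement on outliers. The same section aims for 25 participants and recruits 30. The difference is explained only as a 20% drop-out allowance.

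Other sections bear on how the rule would work:

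- *Outcome parameters*: "Individual participant data will be expressed as average per condition". Each person therefore has four values for the primary outcome (frontal knee range of motion) and four for the secondary outcome.
- *Statistical analysis*: for the four conditions, "a one-factorial analysis of variance with repeated measures will be used", followed by contrasts, with two-sided alpha 0.05 and Holm correction. Ramp and treadmill are compared by paired t-test and "tested for agreement using ICC [3.1, absolute agreement, single measures". The section mentions neither outliers nor a sensitivity analysis.
- *Study goals and objectives*: a tertiary alternative hypothesis is that agreement "between decline ramp walking and speed-matched decline treadmill walking is at least 0.75 (ICC".
- *Examination Procedures*: "Five level walking trials will be captured to evaluate if gait pattern is physiological or not".
- *Limitations and problems anticipated*: the "continuous quality of declined treadmill force plate data cannot be guaranteed".
- *Trial design*: a modified CONSORT chart will report how many people were analysed.

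**The concern.** The rule removes whole people, yet several readings fit its wording. The 2 SD could apply to the participant's mean over conditions, to any condition value against that condition's SD, to any condition value against a pooled SD, to the ramp-treadmill difference, or to the level-walking trials. These readings remove different people and have different effects. Because researchers are not blinded, a reading settled after the data are seen could not be shown to be independent of the results.

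The cut is also mild: about 1 in 22 clean normal values lies beyond 2 SD. Followed as written, the rule is likely to discard valid healthy participants. The flow chart would show how many were analysed, but not how the results would look with everyone included.

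**Working it through.** **Inputs from the documents.** n = 30 recruited, 25 targeted, four conditions with one average each, threshold 2 SD, alpha 0.05, ICC criterion 0.75.

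**Assumptions, not in the documents.** Normal data without measurement faults; no condition effect; equal between-condition correlation r from 0.5 to 0.95; one pass per outcome using the sample's own mean and SD; 0.75 judged on the point estimate.

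**1. The plan's own figure.** 25 × 1.20 = 30, as stated, so the margin is 30 − 25 = 5 people. (Dividing by 0.80 gives 31.25, a separate minor matter.)

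**2. One value per person.** 2 × (1 − Φ(2)) = 0.0455, and 0.0455 × 30 = 1.37 with a known SD. With the sample's own SD the expectation is 1.19. The chance of removing at least one valid person is 82%.

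**3. Four values per person.** Simulation with 20,000 replicates; figures are for r = 0.5 / 0.8 / 0.95:

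| Reading | Mean removed of 30 | Chance fewer than 25 remain | F-test error under no effect |
|---|---|---|---|
| No exclusion | 0 | 0 | 4.8% / 5.2% / 4.8% |
| Participant mean | 1.2 throughout | about 0 | 4.8% / 5.2% / 4.8% |
| Level-walking value | 1.2 throughout | about 0 | 4.9% / 5.2% / 4.8% |
| Any condition, its own SD | 3.83 / 2.83 / 1.94 | 9.6% / 0.9% / 0.0% | 8.6% / 6.6% / 5.2% |
| Any condition, pooled SD | 4.28 / 3.17 / 2.15 | 17.4% / 2.0% / 0.0% | 5.1% / 5.2% / 4.8% |

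The Monte Carlo standard error near 5% is √(0.05 × 0.95 / 20,000) = 0.15 percentage points. Separate runs of the condition-specific reading gave 8.4% at r = 0.5 and 6.2% to 6.4% at r = 0.8, so about 8.5% and 6.5% are fair summaries. Under either any-condition reading, the chance of removing at least one valid person is 96% to over 99%.

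The readings differ for a reason. Trimming each condition around its own mean shrinks the residual spread without shrinking the differences between condition means to match. The other three rows treat the conditions alike. Under condition-specific SDs the Holm familywise error of the three contrasts is 7.8% / 6.1% / 4.9%. If the feedback versus internal-focus contrast is tested alone after screening on that same difference, its error is about 10%.

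If one outlying value on any outcome removed a person from everything, the count would be larger. With an illustrative 40 screened values per person, about 7 are lost at r = 0.8 and about 15 at r = 0.5.

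**4. ICC against 0.75.** In outline, ICC = between-person variance / (between-person + setting + error variance). Screening on values narrows the numerator; screening on the difference narrows the error term. For n = 30, two settings without systematic offset, true ICC 0.80:

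| Screened on | Median ICC | Chance the estimate reaches 0.75 |
|---|---|---|
| Nothing | 0.80 | 75% |
| Participant mean | 0.75 | 52% |
| Either setting, its own SD | 0.75 | 49% |
| Either setting, pooled SD | 0.75 | 48% to 49% |
| Level walking, correlation with slope values 0.3 / 0.5 / 0.8 | 0.80 / 0.79 / 0.77 | 73% / 69% / 59% |
| Ramp-treadmill difference | 0.84 | 87% |

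Screening only one of the two settings gives 56%. At true ICC 0.75, screening on values or participant means lowers the median to about 0.69. At true ICC 0.90, the estimate still reaches 0.75 in at least 95% of runs. An offset of 0.3 SD between settings lowers the starting point but leaves both directions unchanged.

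**The case against.** The rule is incompletely defined rather than wholly undefined: the threshold and the unit are fixed in advance, and the number analysed will be reported. It also sits beside the gait-pattern criterion, which is judged on level-walking trials. If it is a level-walking screen, it removes about 1.2 people, leaves the F-test alone, and affects the ICC only slightly when level and slope values correlate weakly. This reading is possible, but the text does not state it.

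A reader might infer that the rule always lowers the ICC. The documents do not support that, because they do not say what is screened, and screening the ramp-treadmill difference raises it. The direction also depends on fault-free data, and the limitations section gives a real reason to screen the treadmill force plates. As an assumed illustration at true ICC 0.80, a 4 SD fault in one of 30 people on one device gives a median ICC of 0.63 with everyone kept and 0.75 after setting-specific 2 SD exclusion. Screening for faults is therefore legitimate, but a cut on the value cannot tell a fault from a genuine extreme.

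A reader might also infer that the primary test is generally invalid, or that the sample will fall below 25. Neither follows. The F-test error rises under condition-specific SDs and falls back as r increases, and no figure in the documents fixes r. Under the tabulated readings, 25 or more usually remain from this rule alone, although drop-out draws on the same five places. Finally, the ICC analyses are exploratory, and the plan does not say whether 0.75 applies to the estimate or to its interval.

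**Conclusion.** The point holds in a conditional form. The exclusion lacks its variable, condition, reference SD, number of passes and scope, and no analysis with all participants is planned. On the stated assumptions it removes on average about 1.2 (participant mean) to 4.3 (any condition, pooled SD, r = 0.5) of 30 valid participants per outcome. These figures are not bounds: condition-specific screening gives 4.48 at zero correlation.

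The choice of reading alone moves the chance of meeting the 0.75 criterion, at true ICC 0.80, from about 49% to about 87%, against 75% with no exclusion. For the primary F-test, one plausible reading does not hold the 5% level: about 8.5%, 6.5% and 5% at r = 0.5, 0.8 and 0.95. Participant-mean, pooled-SD and level-walking screening leave it at about 5%.

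This should be fixed before analysis. It is not fatal to the primary aim. The gap in the wording is certain; the size of the consequences is not.

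**What to change.** 1. Remove the 2 SD exclusion from the primary analysis.
2. Exclude data only for documented technical failure, such as marker loss or invalid force-plate contact, judged without reference to the outcome value or the condition.
3. Make the analysis of all other participants primary for the ANOVA, the contrasts and the ICC.
4. Report the 2 SD exclusion only as a sensitivity analysis, with its variable, condition, reference SD, number of passes and scope (one outcome or all) fixed in advance.
5. If the rule was meant as a level-walking screen, say so and name the variable and the reference SD.

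The cost is protocol wording and one extra analysis. Genuine extremes and undetected faults stay in the primary analysis, so intervals may be slightly wider; the sensitivity analysis will show whether that matters.

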## Recruitment, informed consent and randomization

Students and staff of the FH Campus Wien – University of Applied Sciences will be addressed with the study information via in-house corridor monitors and an email newsletter. If interested, they may contact the primary investigator. A research team member will check eligibility and provide study details. An assessment date will be agreed in case of willingness and eligibility of the potential participant. Written informed consent will be obtained from the participants prior to the assessments. The participants will randomly be assigned to one of the three sequences, by means of a prepared sequence list as derived from a random sequence generator online tool. Due to the nature of the studied conditions, it will neither be possible to conceal the allocation, nor to blind participants or researchers. A participant will pass through all assessments within one day. Shopping vouchers of 30 € will be offered as incentive for participation.

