## Methods/Design

### Trial design

The study is set up as cross-sectional observation of gait under four conditions, which follows a randomized sequence in order to avoid carry over effects. Chronologically, the assessments will start with the tertiary observation, investigating agreements between declined/inclined ramp and treadmill walking. Thereafter, three out of four conditions (self-paced walking, self-paced walking with internal focus of attention, and self-paced walking with real-time feedback) are tested under block randomization of their six possible permutations (ABC, BCA, CAB, CBA, ACB, BAC). With three conditions ( $n=3$ ), this represents the smallest number of permutations, equaling a Williams design, where each condition precedes each other condition equally often and each treatment occurs equally

frequently at each position. The fourth corresponding condition (speed-matched walking), can technically not take place before the corresponding real-time feedback condition, and is therefore exempted from the sequence randomization and always follows after self-paced walking with real-time feedback. Numbers of participants assessed for eligibility, allocated to assessments, and analyzed will be recorded by a modified CONSORT flow chart, without consideration of losses to follow-up, due the cross-sectional study design. Figure 1 illustrates a flowchart of the trial design.

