#### *Self-paced decline walking*

The participants will be instructed to walk on the declined treadmill with self-selected speed. They will complete a five-minute familiarization period and a three-minute measurement period. Within the measurement phases, three times a period of 20 seconds of self-paced walking will be recorded.

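### The design section randomises over six condition orders, but the randomisation section assigns one of three, and no three orders give the Williams balance the plan claims

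*Combined protocol and SAP*

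**What the plan says.** Under Trial design, self-paced walking (A), internal focus of attention (B) and real-time feedback (C) are tested under "block randomization of their six possible permutations (ABC, BCA, CAB, CBA, ACB, BAC"). The section adds that "this represents the smallest number of permutations, equaling a Williams design", "where each condition precedes each other condition equally often and each treatment occurs equally" often at each position. The stated purpose of the randomised order is to avoid carry-over. Speed-matched walking (D) is not randomised; it "always follows after self-paced walking with real-time feedback".

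Under Recruitment, informed consent and randomization, the assignment rule reads: "The participants will randomly be assigned to one of the three sequences, by means of a prepared sequence list". It names no orders. Under Examination Procedures, "the three following tasks will be performed in the order as specified in the sequence list", with no number of sequences given.

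The Statistical analysis section plans a one-factor repeated-measures ANOVA with pre-specified contrasts and mentions no period, sequence or carry-over term.

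**The concern.** The number of sequences is a rule by which the trial randomises, and the protocol gives two values for it. The design section's case for six is explicit: six is the smallest set with the balance it wants. A list of three would therefore fail the plan's own criterion.

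The balanced orders are the main planned protection against carry-over. All assessments take place within one day, and the feedback condition directs attention to frontal knee alignment, which is what the primary outcome measures. If the orders are unbalanced and the analysis has no term for order, any residual carry-over goes straight into the condition means and the contrasts built from them.

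**Working it through.** **Inputs.** Six listed orders, the balance definition and the fixed place of D (Trial design); three sequences (Recruitment, informed consent and randomization); 30 participants (Sample size estimation and study population); contrasts bc versus d, bc versus a and c versus b (Study goals and objectives). I take A, B, C to be conditions a, b, c, and bc to be the mean of b and c.

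**Step 1: reproduce the plan's figure of six.** Three conditions have 3! = 6 orders, and the list is exactly those six.

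- Position: each condition falls 6/3 = 2 times at each position.
- Immediate precedence: 6 × 2 = 12 neighbour pairs over 6 ordered pairs, 2 each.
- Precedence anywhere: 6 × 3 = 18 pairs over 6 ordered pairs, 3 each.

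There are 6 + 15 + 20 + 15 + 6 = 62 sets of one to five distinct orders. None has both position balance and immediate-precedence balance. The claim that six is the smallest number is correct.

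**Step 2: test three orders.** There are 20 sets of three distinct orders.

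- Precedence anywhere: 3 × 3 = 9 pairs over 6 ordered pairs is 1.5 each, which is impossible. Each pair of conditions occurs once per order, so three orders must split it 2:1 or 3:0. Sets balanced: 0 of 20.
- Immediate precedence: 3 × 2 = 6 pairs would need 1 each. No set achieves this: 0 of 20.
- Position: 2 of 20, namely ABC/BCA/CAB and CBA/ACB/BAC. In the first, AB, BC and CA occur twice each as neighbours and BA, CB and AC never. The second is the mirror image.

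Unequal allocation does not help. Over all splits of 30 participants across three orders, immediate precedence never balances. Precedence anywhere balances only when one order gets 0 participants and two mirror-image orders get 15 each, and position balance then fails.

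**Step 3: effect on the contrasts.** Insert D directly after C and assume that only the immediately preceding condition carries over, with none into the first task. Let w(x,p) be the share of participants in whom condition p comes immediately before condition x, and let k(x) be the contrast coefficients. The weight of carry-over from p in a contrast is Σₓ k(x)·w(x,p). The total absolute weight T is the sum of the absolute values of these over p.

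Six orders (walked as ABCD, BCDA, CDAB, CDBA, ACDB, BACD): A follows B in 1/3 and D in 1/3; B follows A in 1/3 and D in 1/3; C follows A in 1/3 and B in 1/3; D always follows C.

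- c − b: B +1/3, D −1/3, A 0; T = 2/3.
- bc − a: A +1/3, B 1/6 − 1/3 = −1/6, D 1/6 − 1/3 = −1/6; T = 2/3.
- bc − d: A +1/3, B +1/6, D +1/6, C −1; T = 5/3.

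Three orders ABC/BCA/CAB (walked as ABCD, BCDA, CDAB): A follows D in 2/3, B follows A in 2/3, C follows B in 2/3, D follows C always.

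- c − b: B +2/3, A −2/3; T = 4/3.
- bc − a: A +1/3, B +1/3, D −2/3; T = 4/3.
- bc − d: A +1/3, B +1/3, C −1; T = 5/3.

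All 20 three-order sets:

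| Contrast | T, six orders | T, three orders (number of sets) | Higher / equal / lower than six |
|---|---|---|---|
| 3: c − b | 2/3 | 4/3 (6), 1 (6), 2/3 (6), 1/3 (2) | 12 / 6 / 2 |
| 2: bc − a | 2/3 | 4/3 (2), 7/6 (2), 1 (4), 5/6 (6), 2/3 (4), 1/3 (2) | 14 / 4 / 2 |
| 1: bc − d | 5/3 | 11/6 (4), 5/3 (12), 3/2 (4) | 4 / 12 / 4 |

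Taking contrasts 2 and 3 together, 18 of 20 sets exceed six orders on at least one. The two sets at 1/3 on c − b are at 7/6 on bc − a, and the two at 1/3 on bc − a are at 4/3 on c − b. The remaining two, ABC/BCA/BAC and CAB/CBA/ACB, match six orders on both but lose equal positions.

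**The case against.** The strongest reply is that this is a wording slip. The design section lists all six orders and explains why six; the randomisation section names none, and exactly three tasks are randomised, so *three* is easily written for *six*. That is plausible and cannot be excluded: neither the sequence list nor the flow diagram can be seen in the available text. It does not remove the contradiction, because the sentence is the operating instruction for assignment and a reader cannot tell which rule was applied.

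Second, the harm is doubly conditional. It needs a list that really holds three orders, and carry-over that outlasts the familiarisation before each measurement ("They will complete a five-minute familiarization period and a three-minute measurement period"). This stands: the documents settle neither condition.

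Third, T is a worst case, with equal-sized carry-overs acting in adverse directions. If carry-over were the same whatever condition came before, the weights would add with sign. They then sum to 0 on contrasts 2 and 3 for six orders, and also for 8 of the 20 three-order sets, including both position-balanced ones. This also stands, so T should not be read as an expected bias. Nor is there any reason to think the 20 sets equally likely.

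Fourth, contrast 1 is little affected, and six orders are not free of carry-over either: because D always follows C, C never comes immediately before A or B as walked, and T is 2/3 rather than 0. The protocol acknowledges under Limitations that D is not randomised. Drop-out and outlier exclusions may also disturb equal numbers per sequence. All of this is true, but it limits the size of the consequence and leaves the inconsistency in place.

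**Conclusion.** The concern holds. The protocol contradicts itself on the number of sequences, and no three orders, however participants are split among them, can have the balance that the design section states. Both conclusions are certain from the text and the enumeration.

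What a three-order list would do to the results is less certain. On the worst-case measure, the carry-over weight in contrasts 2 and 3 would lie between 1/3 and 4/3, against 2/3 with six orders, depending on the set. This assumes first-order carry-over, D immediately after C, and unadjusted condition means. The protocol gives no carry-over size, so no bias in degrees follows. If the list already holds all six orders, only the sentence is wrong. It should be corrected before the first participant is assigned.

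**What to change.** In Recruitment, informed consent and randomization, change the assignment rule to one of the six sequences, block-randomised as in Trial design, and state the block size, which the protocol does not give. Blocks of six would be one choice: 30/6 = 5 complete blocks, five participants per sequence. The target of 25 analysed participants is not a multiple of six (25 = 4 × 6 + 1), so exact balance holds for those randomised and need not hold for those analysed.

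Check the prepared list against the six permutations before the first participant, and regenerate it if it holds only three. If enrolment has begun, establish which list was used and report it. The cost is one sentence and possibly a new list, with no extra participants or visits.
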